Table	14.2.4.7	Summary of Krebs von den Lungen-6 (KL-6) and change from baseline in Krebs von den Lungen-6 (KL-6) by visit during 24 weeks of treatment by aPAP severity		X					
Table	14.2.4.8	Summary of Carcinoembryonic antigen (CEA) and change from baseline in Carcinoembryonic antigen (CEA) by visit during 24 weeks of treatment		X					
Table	14.2.4.9	Summary of Surfactant Protein A (SP-A) and change from baseline in Surfactant Protein A (SP-A) by visit during 24 weeks of treatment		X					
Table	14.2.4.10	Summary of Surfactant Protein A (SP-B) and change from baseline in Surfactant Protein A (SP-B) by visit during 24 weeks of		X					

			SCR	DB-FAS	DB-PPS	DB-SAF	FU-FAS	FU-MOL INT	FU-SAF
		treatment							
Table	14.2.4.11	Summary of Surfactant Protein A (SP-C) and change from baseline in Surfactant Protein A (SP-C) by visit during 24 weeks of treatment		X					
Table	14.2.4.12	Summary of Surfactant Protein A (SP-D) and change from baseline in Surfactant Protein A (SP-D) by visit during 24 weeks of treatment		X					
Table	14.2.4.13	Summary of Cytokeratin 19 Fragment (Cyfra 21-1) and change from baseline in Cytokeratin 19 Fragment (Cyfra 21-1) by visit during 24 weeks of treatment		X					
Table	14.2.4.14	Summary of Lactate Dehydrogenase (LDH) and change from baseline in Lactate Dehydrogenase (LDH) by visit during 24 weeks of treatment		X					
Table	14.2.4.15	Summary of anti-drug antibodies (anti-GM-CSF, anti-Polyethylene glycol (anti-PEG) and anti-recombinant Human Albumin (anti-rHA) by visit during 24 weeks of treatment		X					
Table	14.2.4.16	Summary of anti-drug antibodies (France only) (anti-GM-CSF, anti-Polyethylene glycol (anti-PEG) and anti-recombinant Human Albumin (anti-rHA) by visit during 24 weeks of treatment		X					
Table	14.2.4.17	Summary of GM-CSF pre- and post-dose at baseline and after 4-weeks of treatment and change from pre-dose at baseline in GM-CSF during 24 weeks of treatment		X					
Table	14.2.4.18	Summary of GM-CSF at baseline and after 4-weeks of treatment in pre-dose and repeated post dose (in Japan only) during 24 weeks of treatment		X					
Table	14.2.4.19	Summary of GM-CSF pre- and post-dose at baseline, after 4, 12 and 24 weeks of treatment and change from pre-dose at baseline in GM-CSF (in US only) during 24 weeks of treatment		X					
Table	14.2.4.20	Summary of number and percentage of subjects in need for oxygen supplement therapy during 24-weeks treatment		X					
Table	14.2.4.21	Analysis of number of subjects in need for oxygen supplement therapy during 24-weeks treatment (Logistic regression)		X					
Table	14.2.4.22	Summary of DSS at Screening and at Week 24		X					
Table	14.2.4.23	Shift tables for DSS at Screening and at Week 24		X					
Table	14.2.4.24	Summary of number and percentage of subjects with DSS 1 or 2 at Screening and at Week 24		X					
Table	14.2.4.25	Shift tables for subjects with DSS 1 or 2 at Screening and at Week 24		X					
		Exploratory Efficacy Endpoints Follow-Up Period							
Table	14.2.5.1	Summary of number of subjects in need of WLL or other treatment during 48-weeks follow-up					X	X	
Table	14.2.5.2	Summary of number of subjects in need of WLL or other treatment during 48-weeks follow-up by visit and type of treatment					X	X	
Table	14.2.5.3	Life table summary of time from start of Follow-up need for WLL or other treatment during Follow-up					X	X	
Figure	14.2.5.4	Kaplan – Meier plot for time from start of Follow-up need for WLL or other treatment during Follow-up					X	X	
Table	14.2.5.5	Summary of and change from baseline in (A-a)DO2 during 48-weeks follow-up by visit					X	X	
Table	14.2.5.6	Summary and change from baseline in (A-a)DO2 by visit (including only samples for arterial blood gas) during 48-weeks follow-up by visit					X	X	
Table	14.2.5.7	Summary of and change from baseline in VC (% predicted) during 48-weeks follow-up by visit					X	X	
Table	14.2.5.8	Summary of and change from baseline in DLCO (% predicted) during 48-weeks follow-up by visit					X	X	

			SCR	DB-FAS	DB-PPS	DB-SAF	FU-FAS	FU-MOL INT	FU-SAF
Table	14.2.5.9	Summary of and change from baseline in FEV1 (% predicted) during 48-weeks follow-up by visit					X	X	
Table	14.2.5.10	Summary of and change from baseline in FVC (% predicted) during 48-weeks follow-up by visit					X	X	
Table	14.2.5.11	Summary of and relative change from baseline of PaO2 during 48-weeks follow-up by visit					X	X	
Table	14.2.5.12	Summary of number of subjects with improved tolerance to exercise (increase in distance walked \geq 50 m) during 48-weeks follow-up by visit					X	X	
Table	14.2.5.13	Summary of number of subjects with improved tolerance to exercise (desaturation <4 percentage points on the 6MWT) during 48-weeks follow-up by visit					X	X	
Table	14.2.5.14	Summary of Borg CR10 pre post and corresponding difference in walk dyspnoea score and change from baseline in scores during 48-weeks follow-up by visit					X	X	
Table	14.2.5.15	Summary of cough (VAS) scores and change from baseline in cough scores during 48-weeks follow-up by visit					X	X	
Table	14.2.5.16	Summary of SGRQ dimension scores and corresponding changes from baseline during 48-weeks follow-up by visit					X	X	
Table	14.2.5.17	Summary of EQ-5D-5L dimension scores and corresponding shifts from baseline during 48-weeks follow-up by visit					X	X	
Table	14.2.5.18	Summary of levels of and change from baseline in anti-GM-CSF after 12 and 24 weeks of follow-up by visit					X	X	
Table	14.2.5.19	Summary of GM-CSF pre- and post-dose during Follow-up (US only)					X	X	
Table	14.2.5.20	Summary of DSS at during 48-weeks follow-up by visit					X	X	
Table	14.2.5.21	Shift tables for DSS during 48-weeks follow-up by visit					X	X	
Table	14.2.5.22	Summary of number and percentage of subjects with DSS 1 or 2 during 48-weeks follow-up by visit					X	X	
Table	14.2.5.23	Shift tables for subjects with DSS 1 or 2 during 48-weeks follow-up by visit					X	X	
Table	14.2.5.24	Summary of details related to WLLs including reasons for, one or both lungs, and saline volume used during 48-weeks follow-up.					X	X	
Exposure									
Table	14.2.6.1	Extent of Exposure		X	X	X	X	X	X
Table	14.2.6.2	Extent of Exposure by Age Group				X			
Table	14.2.6.3	Extent of Exposure by Sex				X			
Table	14.2.6.4	Extent of Exposure by by aPAP severity				X			
Table	14.2.6.5	Extent of Exposure by aPAP diagnosis				X			
Table	14.2.6.6	Extent of Exposure by previous WLL				X			
Table	14.2.6.7	Compliance		X	X	X	X	X	X
Table	14.2.6.8	Concomitant Medication				X			X
14.3 SAFETY DATA									
Displays of Adverse Events									
Table	14.3.1.1	Summary of adverse events during 24 weeks of treatment				X			
Table	14.3.1.2	Adverse events by system organ class and preferred term during 24 weeks of treatment				X			

			SCR	DB-FAS	DB-PPS	DB-SAF	FU-FAS	FU-MOL INT	FU-SAF
Table	14.3.1.3	Adverse events: Number of subjects by severity and relationship to treatment during 24 weeks of treatment				X			
Table	14.3.1.4	Summary of serious adverse events during 24 weeks of treatment				X			
Table	14.3.1.5	Serious adverse events by system organ class and preferred term during 24 weeks of treatment				X			
Table	14.3.1.6	Serious adverse events: Number of subjects by severity and relationship to treatment during 24 weeks of treatment				X			
Table	14.3.1.7	Adverse events by system organ class and preferred term during 24 weeks of treatment by Age Groups				X			
Table	14.3.1.8	Adverse events by system organ class and preferred term during 24 weeks of treatment by Sex				X			
Table	14.3.1.9	Summary of adverse events in total and during 48 weeks of follow-up							X
Table	14.3.1.10	Adverse events by system organ class and preferred term in total and during 48 weeks of follow-up							X
Table	14.3.1.11	Adverse events: Number of subjects by severity and relationship to treatment total and during 48 weeks of follow-up							X
Table	14.3.1.12	Summary of serious adverse events during total and during 48 weeks of follow-up							X
Table	14.3.1.13	Serious adverse events by system organ class and preferred term total and during 48 weeks of follow-up							X
Listings of Deaths Other Serious and Significant Adverse Events									
Listing	14.3.2.1	List of deaths				X			X
Listing	14.3.2.2	List of other serious adverse events				X			X
Listing	14.3.2.3	List of adverse events leading to treatment and/or trial discontinuation				X			X
Laboratory Data									
Listing	14.3.4.1	Laboratory reference ranges	X						
Listing	14.3.4.2	Abnormal laboratory Value Listing				X			X
Table	14.3.5.1	Summary of haematology laboratory measurements and corresponding changes from baseline by visit during 24 weeks of treatment				X			
Table	14.3.5.2	Shift tables for haematology laboratory measurements from baseline by visit during 24 weeks of treatment				X			
Table	14.3.5.3	Summary of biochemistry laboratory measurements and corresponding changes from baseline by visit during 24 weeks of treatment				X			
Table	14.3.5.4	Shift tables for biochemistry laboratory measurements from baseline by visit during 24 weeks of treatment				X			
Table	14.2.5.5	Summary of urinalysis laboratory measurements (France only) by visit during 24 weeks of treatment				X			
Table	14.3.5.6	Summary of haematology laboratory measurements and corresponding changes from baseline by visit during 48 weeks of follow-up							X
Table	14.3.5.7	Shift tables for haematology laboratory measurements from baseline by visit during 48 weeks of follow-up							X
Table	14.3.5.8	Summary of biochemistry laboratory measurements and corresponding changes from baseline by visit during 48 weeks of follow-up							X
Table	14.3.5.9	Shift tables for biochemistry laboratory measurements from baseline by visit during 48 weeks of follow-up							X
Table	14.3.5.10	Summary of urinalysis laboratory measurements (France only) by visit during 48 weeks of treatment							X

			SCR	DB-FAS	DB-PPS	DB-SAF	FU-FAS	FU-MOL INT	FU-SAF
Other Safety Data									
Table	14.3.6.1	Summary of vital signs and change from baseline in vital signs by visit during 24 weeks of treatment				X			
Table	14.3.6.2	Shift tables for changes in vital signs from baseline by visit during 24 weeks of treatment				X			
Table	14.3.6.3	Shift tables for changes in Physical examination from baseline by visit during 24 weeks of treatment				X			
Table	14.3.6.4	Summary of ECG and change from baseline in ECG by visit during 24 weeks of treatment full analysis set				X			
Table	14.3.6.5	Shift tables for changes in ECG from baseline by visit during 24 weeks of treatment				X			
Table	14.3.6.6	Summary of adverse findings in CT at week 24 compared to baseline				X			
Table	14.3.6.7	Summary of vital signs and change from baseline in vital signs by visit during 48 weeks of follow-up							X
Table	14.3.6.8	Shift tables for changes in vital signs from baseline by visit during 48 weeks of follow-up							X
Table	14.3.6.9	Shift tables for changes in Physical examination from baseline by visit during 48 weeks of follow-up							X
Table	14.3.6.10	Summary of ECG and change from baseline in ECG by visit during 48 weeks of follow-up							X
Table	14.3.6.11	Shift tables for changes in ECG from baseline by visit during 48 weeks of follow-up							X
Listing	16.1.7	Randomization Scheme		X					

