7 INVESTIGATIONAL PLAN

7.1 Trial Design and Plan-Description

A Screening Visit will be conducted 14 days (± 7 days) prior to the Baseline Visit to determine eligibility. Subjects with aPAP confirmed to be stable or progressive during a period of at least two months prior to the Baseline Visit will be eligible for treatment. Subjects are not eligible for treatment if spontaneous remission has occurred during this two-month period, defined as absolute VC improved by more than 5% and/or DLCO improved by more than 10%.

At the Baseline Visit, eligible subjects will be randomised to receive treatment for up to 24 weeks with either:

- 1) inhaled molgramostim (300 μg) administered once daily,
- 2) inhaled molgramostim (300 μg) and matching placebo administered intermittently (12 cycles of seven days molgramostim, seven days placebo; both administered once daily) or
- 3) inhaled placebo administered once daily.

[figure not shown]
The trial will include two phases; a Double-blind treatment period consisting of up to eight trial visits (Screening, Baseline, and at Weeks 4, 8, 12, 16, 20 and 24 after randomisation) and an open-label treatment Follow-up period consisting of up to five trial visits (at Weeks 4, 12, 24, 36 and 48 post-treatment). The 36 and 48-weeks post treatment visits are only applicable for subjects included before amendment 11 to the protocol was approved by the national authorities in the country where the subject originates from.

Participating subjects will be encouraged to contact the clinic between visits if they experience AEs or have any concerns (*Figure 1*).

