- Number of subjects with improved QoL (reduction of ≥4 units on the SGRQ) after 4, 12, and 24-weeks treatment
- Number of subjects with 'no problems' in EQ-5D-5L after 4, 12, and 24-weeks treatment
- Change from baseline in serum concentration of biomarkers: Krebs von den Lungen-6 (KL-6), Carcinoembryonic antigen (CEA), Surfactant Protein A (SP-A), Surfactant

Protein B (SP-B), Surfactant Protein C (SP-C), Surfactant Protein D (SP-D), Cytokeratin 19 Fragment (Cyfra 21-1) and Lactate Dehydrogenase (LDH) after 4, 12, and 24-weeks treatment

- Anti Granulocyte Macrophage Colony Stimulating Factor (GM-CSF) antibody titers after 4, 12 and 24-weeks treatment
- Change in serum concentration of GM-CSF post first dose of trial drug and after 4-weeks of treatment
- Number of subjects in need for oxygen supplement therapy during 24-weeks treatment.
- The distribution of DSS at Screening and at Week 24
- The percentage of subjects with DSS 1 or 2 at Screening and at Week 24.

Follow-up period

- Number of subjects requiring WLL or other treatment for aPAP and number of treatment courses required during 48-weeks follow-up.
- Time to WLL, or other treatment for aPAP during 48-weeks follow-up.
- Absolute change from baseline in (A-a)DO₂ and VC (% predicted), DLCO (% predicted), FEV₁(% predicted) , FVC (% predicted), and and relative change from baseline of PaO₂ after 12, 24, 36 and 48-weeks follow-up
- Number of subjects with improved tolerance to exercise (increase in distance walked ≥50 m or desaturation <4 percentage points on the 6MWT) after 12, 24, 36 and 48-weeks follow-up
- Number of AEs, severe AEs, SAEs and ADRs , including clinically significant changes in laboratory tests and ECG variables, during 48-weeks follow-up
- Levels of anti-GM-CSF after 12 and 24 weeks follow-up.
- The distribution of DSS after 24 and 48-weeks follow-up
- The percentage of subjects with DSS 1 or 2 after 24 and 48-weeks follow-up.

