3 OVERALL STUDY DESIGN

3.1 Overview of Study Design

[figure not shown]
This is a parallel, double-blind, multicentre, randomised clinical trial in autoimmune pulmonary alveolar proteinosis subjects, where a planned total of 135 subjects (see section 3.2) are stratified according to whether or not a WLL has been conducted within 2 months prior to the Baseline (according to protocol version 4.0 and later versions), or whether or not

WLL was conducted between the screening visit and the randomization visit (according to protocol versions before version 4.0). Subjects will be randomised 1:1:1 to receive treatment for up to 24 weeks with either;

- 1) Inhaled molgramostim (300 µg) administered once daily,
- 2) Inhaled molgramostim (300 µg) and matching placebo administered intermittently (12 cycles of seven days molgramostim, seven days placebo; both administered once daily) or
- 3) Inhaled placebo administered once daily.

The trial includes two phases; a Double-blind treatment period consisting of up to eight trial visits (Screening, Baseline, and at Weeks 4, 8, 12, 16, 20 and 24 after randomisation) and a Follow-up period consisting of up to five trial visits (at Weeks 4, 12, 24, 36 and 48 post-treatment). During the follow-up period all subjects recruited under protocol version 4.0 or later versions will receive treatment with inhaled molgramostim (300 µg) administered once daily in an intermittent regimen for 24 weeks (12 cycles of seven days molgramostim, seven days off). Patients recruited under protocol version 2.0 were only to receive treatment in the follow-up period in case of worsening of aPAP, and patients recruited under protocol version 3.0 were treated (if needed) using the intermittent regimen for 24 weeks and according to investigator’s discretion for 24 additional weeks. Likewise, the 36 and 48-weeks post treatment visits are only applicable for subjects included before approval of protocol version 4.0.

Figure 1 Overall Trial Design

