- Number of subjects requiring WLL, or other treatment for aPAP and number of treatment courses required during 24 and 48-weeks follow-up
- Time to WLL, or other treatment for aPAP during 24 and 48 weeks follow-up
- Absolute change from baseline in (A-a)DO₂ and VC (% predicted), DLCO (% predicted), FEV₁ (% predicted), FVC (% predicted), and relative change from baseline of PaO₂ after 12, 24, 36 and 48-weeks follow-up
- Number of subjects with improved tolerance to exercise (increase in distance walked ≥50 m (compared to baseline) or desaturation <4 percentage points on the 6MWT, respectively) after 12, 24, 36 and 48-weeks follow-up
- Levels of anti-drug antibodies (anti-GM-CSF, anti-Polyethylene glycol (anti-PEG) and anti-recombinant Human Albumin (anti-rHA)) after 12 and 24 weeks follow-up
- The distribution of DSS after 24 and 48-weeks follow-up
- The percentage of subjects with DSS 1 or 2 after 24 and 48-weeks follow-up

In addition to the above endpoints described in the protocol, (A-a)DO₂ values collected during the follow-up period will be summarised only including values assessed based on arterial blood gas samples, excluding capillary samples.

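### Follow-up AE and SAE tables titled 48 weeks pool subjects followed for 24 weeks with subjects followed for 48, so their crude percentages estimate neither risk

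*SAP*

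**What the plan says.** **Follow-up length.** Protocol 7.1 states: "The 36 and 48-weeks post treatment visits are only applicable for subjects included before amendment 11 to the protocol was approved by the national authorities". Protocol 7.4 accordingly puts the last visit at Visit 11 (follow-up Week 24) or Visit 13 (follow-up Week 48). SAP 3.1 makes the same distinction by protocol version: "the 36 and 48-weeks post treatment visits are only applicable for subjects included before approval of protocol version 4.0". That amendment 11 and version 4.0 mark the same change is my inference from these two sections.

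**AE and SAE outputs.** SAP Appendix 1, section 14.3, lists five follow-up tables (14.3.1.9 to 14.3.1.13), all marked for FU-SAF only. Examples are "Adverse events by system organ class and preferred term in total and during 48 weeks of follow-up" and "Serious adverse events by system organ class and preferred term total and during 48 weeks of follow-up". SAP 4 does not restrict FU-SAF by planned follow-up length. SAP 5.3.11 specifies numbers of subjects and of events, and SAP 5.3.3 specifies counts and percentages for categorical data.

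**Endpoint wording.** Protocol 10.2.3.2 defines the follow-up AE endpoint over 24 or 48 weeks. SAP 2.2 keeps only the longer horizon: "including clinically significant changes in laboratory tests and ECG variables, during 48-weeks follow-up". SAP 2.3 does the same for the additional safety variables. SAP 5.1, which lists departures from the protocol, does not mention this. The SAP's own follow-up safety objective (section 2) still names both durations.

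**Whole lung lavage (WLL).** SAP 5.3.8 plans "Number of subjects requiring WLL, or other treatment for aPAP and number of treatment courses required during 24 and 48-weeks follow-up". Appendix 1 has a count table, 14.2.5.1 ("Summary of number of subjects in need of WLL or other treatment during 48-weeks follow-up"), a by-visit table (14.2.5.2), "Life table summary of time from start of Follow-up need for WLL or other treatment during Follow-up" (14.2.5.3) and a Kaplan-Meier plot (14.2.5.4). All are produced for both FU-FAS and FU-MOL-INT.

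**The concern.** A crude percentage titled 48 weeks invites the reader to take it as a 48-week incidence. Here part of the denominator could not contribute an event after Week 24, by design. The figure is a weighted average of a 24-week risk and a 48-week risk, with weights set by how many subjects were included before each country approved the amendment. It would change if enrolment had run faster or slower, with nothing different about the drug.

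The two groups also differ in follow-up treatment. Under SAP 3.1, subjects recruited from version 4.0 on all receive 24 weeks of intermittent open-label molgramostim. Version 2.0 subjects were treated only on worsening. Version 3.0 subjects were treated if needed, and at the investigator's discretion for the second 24 weeks. All experience in Weeks 24-48 therefore comes from subjects whose follow-up treatment was optional.

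At stake is the absolute incidence of AEs and SAEs in the trial's longer-term safety data. In an open-label phase where every arm can receive active drug, absolute incidence is what most readers will look for.

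**Working it through.** The documents give no follow-up incidence, no person-time and no count of subjects on each schedule, so there is no planned figure to reproduce. The check has two parts.

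**1. Direction.** Let f be the share of the denominator with only 24 weeks of follow-up, R24 and R48 the risks by Weeks 24 and 48, and assume these risks are the same in both groups.

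- Crude percentage = f × R24 + (1 − f) × R48
- Shortfall against R48 = f × (R48 − R24)

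The shortfall is positive whenever some subjects stop at Week 24 and some first events occur in Weeks 24-48. No assumption about the shape of the hazard is needed.

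**2. Illustrative size.** Inputs:

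- N = 135, the planned randomised total (SAP 3.1). FU-SAF will be smaller, because SAP 4 requires entry into follow-up with at least one data point.
- Number on the 48-week schedule: 30 to 78, an assumption. The upper value borrows the 78 randomised subjects in SAP Appendix 2, section 1.3. That count was made for a re-estimation planned for January 2018, about seven months after amendment 11 (dated 06 June 2017 in SAP 3.2), and it leaves out withdrawals without WLL. The lower value has no source in the documents. Neither is a bound.
- Constant hazard and no withdrawals, so R24 = 1 − √(1 − R48).

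Then f = 105/135 = 0.778 with 30 on the long schedule, and f = 57/135 = 0.422 with 78.

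For R48 = 20%: R24 = 1 − √0.80 = 10.6%.

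- 30 of 135: 0.778 × 10.6% + 0.222 × 20% = 12.7%
- 78 of 135: 0.422 × 10.6% + 0.578 × 20% = 16.0%

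| True 48-week risk | 24-week risk | Crude, 30 of 135 | Crude, 78 of 135 |
|---|---|---|---|
| 10% | 5.1% | 6.2% | 7.9% |
| 20% | 10.6% | 12.7% | 16.0% |
| 50% | 29.3% | 33.9% | 41.3% |

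Planned follow-up would be (30 × 48 + 105 × 24)/52 = 76 to (78 × 48 + 57 × 24)/52 = 98 person-years. It would be 135 × 48/52 = 125 person-years if everyone had 48 weeks.

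**Sensitivity to the hazard.** Suppose instead that the hazard in Weeks 24-48 is half that in Weeks 0-24. Two thirds of the cumulative hazard then falls before Week 24, so for R48 = 20%, R24 = 1 − 0.80^(2/3) = 13.8%. The crude figure becomes 0.778 × 13.8% + 0.222 × 20% = 15.2%, up to 0.422 × 13.8% + 0.578 × 20% = 17.4%. The direction is unchanged and the gap is smaller.

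**The case against.** **No estimate is claimed.** Follow-up data are descriptive and reported separately (Protocol 12.1 and 13.10), and the tables give counts and percentages without calling them cumulative incidences. SAP 3.1 discloses the two schedules. This stands in part: the percentages understate incidence only if read as the titles invite. But the titles do invite that reading, and SAP 2.2 and 2.3 drop the protocol's two-duration wording.

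**A reader can reconstruct the denominators.** Table 14.1.8 gives subjects by visit for FU-SAF, follow-up exposure is tabulated in 4-weekly intervals (SAP 5.3.9), and AE listings carry relative day. This is true and limits the harm. It also shows that the dates needed for a split already exist. The planned tables still do not make the split.

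**The effect cannot be quantified.** This stands. No document counts inclusions before and after the amendment, and the cut-off is national approval, for which no dates are given. A constant hazard is doubtful because treatment in later follow-up was optional for early subjects.

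**WLL.** A reader might infer that the follow-up WLL results suffer in the same way. The documents do not support that. The methods text plans WLL counts at both horizons, and there are a by-visit table, a life table and a Kaplan-Meier plot, repeated for FU-MOL-INT. The follow-up censoring rule is not written out, but SAP 5.3.8 carries over the double-blind approach, which censors at withdrawal or at the period's last visit. Only the title of Table 14.2.5.1 is loose.

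**Treatment comparisons.** A reader might also infer bias between arms. With 1:1:1 randomisation, inclusion before or after the amendment should be similarly distributed across arms, so comparisons by randomised arm should be little affected.

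**Conclusion.** The point holds for the five AE and SAE tables. As specified, they pool two planned follow-up lengths under a 48-week title and provide no way within the table to separate them. The crude percentages estimate neither the 24-week nor the 48-week risk and, read as titled, understate the latter.

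The direction rests only on some subjects stopping at Week 24, some first events falling later, and comparable risk over time in the two groups. The size is unknown. Reading a true 20% as about 13% to 16% depends on the assumed 30 to 78 of 135 and on a constant hazard, and should not be taken as a documented shortfall.

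Severity is low. The effect is on absolute, descriptive safety percentages. The primary and key secondary analyses belong to the double-blind period and are untouched.

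**What to change.** 1. Add a derived variable for planned follow-up length (24 or 48 weeks), based on whether the subject was included before the amendment took effect nationally.
2. In Tables 14.3.1.9 to 14.3.1.13, present follow-up Weeks 0-24 in all FU-SAF subjects. Present Weeks 24-48 separately, only in subjects on the 48-week schedule and with their own denominator. State in the SAP how the Week 24 cut is made, for example by the date of Visit 11.
3. If person-time rates are added, give them by these two periods. One pooled rate over the whole follow-up would again assume a constant hazard. It would also blend the first 24 weeks with a later period that only early subjects contribute to, and so would still depend on enrolment timing.
4. Change the wording of these tables, SAP 2.2 and 2.3, and Table 14.2.5.1 to 24 or 48 weeks, in line with Protocol 10.2.3.2 and SAP 5.3.8. The other WLL outputs need no change.

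The cost is the one derived variable and revised shells and titles. No new data are needed.
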